#### 11.3.2. Serious Adverse Events

A **serious adverse event** (SAE) is defined as an event that, at any dose, results in the following:

- Death
- Life-threatening (Note: The term “life-threatening” in the definition of “serious” refers to an event in which the subject was at risk of death at the time of the event; it does not refer to an event that hypothetically might have caused death if it had been more severe.)
- In-patient hospitalization or prolongation of existing hospitalization
- Persistent or significant disability/incapacity
- A congenital anomaly/birth defect

- A medically important event or reaction: such events may not be immediately life-threatening or result in death or hospitalization but may jeopardize the subject or may require intervention to prevent one of the other outcomes constituting SAEs. Medical and scientific judgment must be exercised to determine whether such an event is a reportable under expedited reporting rules. Examples of medically important events include intensive treatment in an emergency room or at home for allergic bronchospasm; blood dyscrasias or convulsions that do not result in hospitalization; and development of drug dependency or drug abuse.

### **11.3.3. Special Situations Reports**

Special situation reports include reports of pregnancy, medication error, abuse, misuse, overdose, lack of effect; off-label use, product complaints and occupational exposure.

For instructions on reporting pregnancy, see [11.1.1](#).

Medication error is any unintentional error in the prescribing, dispensing, or administration of a medicinal product while in the control of the health care provider, subject, or consumer.

Abuse is defined as persistent or sporadic intentional excessive use of a medicinal product by a subject.

Misuse is defined as any intentional and inappropriate use of a medicinal product that is not in accordance with the protocol instructions or the local prescribing information.

An overdose is defined as an accidental or intentional administration of a quantity of a medicinal product given per administration or cumulatively which is above the maximum recommended dose as per protocol or in the product labelling (as it applies to the daily dose of the subject in question). In cases of a discrepancy in drug accountability, overdose will be established only when it is clear that the subject has taken the excess dose(s). Overdose cannot be established when the subject cannot account for the discrepancy except in cases in which the investigator has reason to suspect that the subject has taken the additional dose(s).

Lack of effect is defined as the failure of the expected or intended pharmacologic action or therapeutic effect as described in the pharmacology and/or indications section of the current product label.

Off-label use is defined as the intentional use of licensed medicinal product by a Health Care Professional for a medical purpose not in accordance with the authorized product information with respect to indication, dose, route of administration, or patient population (e.g., the elderly).

Product complaint is defined as complaints arising from potential deviations in the manufacture, packaging, or distribution of the medicinal product.

Occupational exposure is defined as exposure to a medicinal product as a result of one's professional or non-professional occupation.

#### **11.3.4. Adverse Drug Reaction**

An adverse drug reaction (ADR) is defined as an untoward medical occurrence (unintended or noxious responses) considered causally related to an investigational or approved medicinal product at any dose administered. Adverse reactions may arise from medication errors, uses outside what is foreseen in the protocol or prescribing information (off-label use), misuse and abuse of the product, overdose, or occupational exposure.

#### **11.3.5. Serious Adverse Drug Reaction**

A serious adverse drug reaction (SADR) is defined as any SAE that is considered causally related to the medicinal product at any dose administered.

#### **11.4. Clinical Laboratory Abnormalities**

Laboratory abnormalities without clinical significance are not recorded as safety events. However, laboratory abnormalities (e.g., clinical chemistry, hematology, and urinalysis) that require medical or surgical intervention or lead to drug interruption, modification, or discontinuation and considered to be causally associated with the medicinal product must be recorded as an AE, or an SAE, if applicable. In addition, laboratory or other abnormal assessments (e.g., electrocardiogram, x-rays, vital signs) that are associated with signs and/or symptoms must be recorded as an AE or SAE if they meet the definition of an AE or SAE as described in Section 11.3. If the laboratory abnormality is part of a syndrome, record the syndrome or diagnosis (e.g., anemia), not the laboratory result (i.e., decreased hemoglobin).

#### **11.5. Assessment of Causality for Study Drugs**

The investigator or qualified sub-investigator is responsible for assessing the causal relationship to drug therapy for each event and using clinical judgment and the following considerations:

- **No:** Evidence exists that the AE has an etiology other than the drug. For SAEs, an alternative causality must be provided (e.g., pre-existing condition, underlying disease, intercurrent illness, concomitant medication).
- **Yes:** There is a reasonable possibility that the event may have been caused by the medicinal product.

It should be emphasized that ineffective treatment should not be considered as causally related in the context of reporting safety information.

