### 9.3. Variables

This is a non-interventional study. Only data available from routine medical care will be collected within the study. All variables collected will be identical in nature and independent of the method of data collection (retrospective/prospective).

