### **9.5. Study Size**

This study aims to include patients who have been or are currently being treated with idelalisib according to the product information and treatment guidelines for the treatment of refractory FL after marketing authorization in the EU (September 2014) and Australia (January 2015).

Prevalence data for iNHL in the EU are limited. HAEMACARE, a European cancer registry-based project on hematologic malignancies funded by the European Commission, provides European incidence rates but not prevalence data {Sant 2010}. Australian prevalence data could not be identified. The Decision Resources Group (<http://www.decisionresourcesgateway.com/index.aspx>) estimated a 10-year limited-duration prevalence for FL in 5 major EU countries (France, Germany, Italy, Spain, and United Kingdom) over the 2011-2021 forecast period based on cancer registry databases in the EU-5. The EU prevalence estimates for FL ranged from 1.4 (Spain) in 2011 to 3.1 (France) per 10,000 in 2015 (RMP, section 1.1.1.4.2).

Based on the pivotal studies 101-09, GS-US-313-0124 and GS-US-313-0125 the median treatment period is estimated to be 8 months, taking into account that studies GS-US-313-0124 and GS-US-313-0125 were terminated early. Thus, a retrospective timeframe of around 3 years and a prospective observation period of another 2.5 years allow data of approximately 300 patient-years to be collected.

A sample size of 300 patient-years is based on the chance to find a proportion of adverse events of 3.2% with a precision of 2%. The table below shows the relationship between various detectable single proportions of AEs and precision of the estimate.

Proportions found in studies 101-09, GS-US-313-0124 and GS-US-313-0125 were 1.4% ( Grade 3 diarrhea and/or colitis), 2.0% (( Grade 3 febrile neutropenia), 6.1% (( Grade 3 infection) and 8.1% (( Grade 3 rash).

Proportion of AEs	3.2%	5.2%	7.6%
Precision	0.02	0.025	0.03

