## 9.7. Data Analysis

Categorical variables will be summarized descriptively by number and percentage of patients in each categorical definition including 95% confidence intervals. Continuous variables will be summarized descriptively by mean, standard deviation, median, lower quartile, upper quartile, minimum and maximum.

Multivariate Poisson regression analyses will be used to estimate rates of ADRs and SADR, adjusted for potential confounders (demographics, baseline disease assessment, medical history, treatment history, treatment changes; see section 9.3).

Multivariate Cox Proportional Hazard analyses will be used to model time-to-event data, and time to ADRs, SADR and AESIs.

Kaplan Meier curves will be used to illustrate time-to-event analyses.

Special focus will be given to the differences in retrospective and prospective data collection. Although not by intention, data might be collected differently in retrospect compared to patient's data that will be collected prospectively. Retrospective patients will be recruited through systematic search of the sites' patient data management system, whereas prospective data will be collected from those patients prescribed idelalisib after the start of the study. Behavioral changes of the site staff after the initiation of the study might play a role in differential data collection. Thus, missing data for the retrospective data might be an issue. Stratified analyses will be conducted to account for this potential bias.

The extent of missing data in the study will be described and tabulated. Imputation methods will be used to account for missing values in the dataset for those variables used in multivariate modeling (demographics, baseline disease assessment, medical history, treatment history) and changes in idelalisib treatment following the current ENCePP guidelines (Methodological Standards in Pharmacoepidemiology: Section 5.3. Handling of missing data;

[http://www.encepp.eu/standards\\_and\\_guidances/methodologicalGuide5\\_3.shtml](http://www.encepp.eu/standards_and_guidances/methodologicalGuide5_3.shtml) {Rubin 1987}, {Moons 2006}, {Welch 2014}. Multiple imputation by chained equations (MICE) as sequential regression multiple imputation will be used handling of missing data {Azur 2011}. Using MICE, missing values are imputed based on the observed values for a given individual and the relationships within the data for other participants.

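### The causality calls that define ADR and SADR are not split into charted at the time and assigned at abstraction, so stratifying by collection mode cannot separate attribution from documentation

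*Protocol*

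**What the plan says.** Section 9.3 makes two statements about the data. The first is "Only data available from routine medical care will be collected within the study". The second is "All variables collected will be identical in nature and independent of the method of data collection (retrospective/prospective".

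Section 11.5 then states: "The investigator or qualified sub-investigator is responsible for assessing the causal relationship to drug therapy for each event". The scale is binary. Yes means "There is a reasonable possibility that the event may have been caused by the medicinal product". No needs evidence of another cause, and for an SAE the alternative must be named. There is no category for an event that cannot be assessed, and no separate rule for events that occurred before data collection began.

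Two outcomes rest on that answer. In section 11.3.4 an ADR is an untoward occurrence "considered causally related to an investigational or approved medicinal product at any dose administered". Section 11.3.5 reads: "A serious adverse drug reaction (SADR) is defined as any SAE that is considered causally related to the medicinal product at any dose administered".

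Section 9.7 models ADR and SADR rates by Poisson regression and time to these events by Cox regression. On the difference between retrospective and prospective collection it says: "Stratified analyses will be conducted to account for this potential bias". Sections 9.7 and 9.9 trace that difference to staff behaviour, missing data and thinner documentation. Section 8 names SAE rates, with a focus on the health outcomes of interest (HOIs).

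**The concern.** A causality answer under a study-specific Yes/No rule is a judgement, and it can depend on when it is made and on what the chart contains. For a prospective event it can be given close to the event. For a retrospective event it may be an opinion written in the chart at the time, or one formed years later by the person abstracting the record. The protocol lets both enter the same variable without a marker.

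Two things are at stake. The pooled ADR and SADR rates may mix two kinds of attribution in unknown proportions. And the stratified analysis, which is the protocol's safeguard against differential collection, would show a difference in ADR or SADR rates without showing whether events were missed or were judged differently. The interim report planned for Q1 2019 is on retrospective data, so its ADR and SADR figures would depend on whichever practice each site adopts.

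**Working it through.** **1. The lag.** Section 9.5 takes patients treated "after marketing authorization in the EU (September 2014) and Australia (January 2015" and describes a retrospective timeframe of around 3 years. Sections 6 and 9.2 put the start of data collection in Q1 2018. Lag = days between the dates / 365.25.

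| Region | From | To | Years |
|---|---|---|---|
| EU, shortest | 30 Sep 2014 | 1 Jan 2018 | 1189/365.25 = 3.26 |
| EU, longest | 1 Sep 2014 | 31 Mar 2018 | 1307/365.25 = 3.58 |
| Australia, shortest | 31 Jan 2015 | 1 Jan 2018 | 1066/365.25 = 2.92 |
| Australia, longest | 1 Jan 2015 | 31 Mar 2018 | 1185/365.25 = 3.24 |

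This agrees with the protocol's own figure of around 3 years. It is the lag for an event right after authorisation that is assessed at the start of data collection. Later events have a shorter lag, and later chart entry lengthens it. If retrospective charts were still being entered at the end of 2018 (an assumption), the EU maximum would be about 4.3 years. The typical lag cannot be derived.

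**2. What the strata can show.** For each stratum let λ be the true SAE rate, d the share of events found in the record, and s the share of those answered Yes. Then:

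- observed all-cause SAE rate = λ·d
- observed SADR rate = λ·d·s

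For retrospective (R) against prospective (P):

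- SAE ratio = (λR/λP)·(dR/dP)
- SADR ratio = (λR/λP)·(dR/dP)·(sR/sP)

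With equal true rates and equal documentation, the SADR ratio reduces to sR/sP. With unequal documentation, one observed SADR ratio cannot be split into dR/dP and sR/sP. If the SAE ratio is reported beside it, dividing the two gives sR/sP directly.

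**3. Size.** The protocol gives no attribution share. If s is assumed to lie between 0.4 and 0.8 in each stratum, sR/sP runs from 0.4/0.8 = 0.50 to 0.8/0.4 = 2.00. For example, 0.6/0.5 = 1.20, 0.5/0.6 = 0.83, and equal shares give 1.00. These figures restate the assumption. They show that either direction is possible and are not an estimate.

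**4. Where attribution decides what is collected.** Section 11.1 collects all SAEs. Apart from special situations and pregnancies, it collects non-serious events only if they led to a dose modification, interruption or discontinuation, or are ADRs. A non-serious pneumonitis without a dose change is an HOI under 9.3, but it enters the data only if judged related. Section 11.4 makes the recording of some laboratory abnormalities conditional on a causal link, which bears on transaminase elevation and neutropenia. All-cause SAEs are therefore the clean contrast. HOIs are clean only where they are collected regardless of attribution.

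**The case against.** The strongest reply is that section 11.5 says who judges, not when. Section 9.4 says abstraction covers all safety information already in the record, which can include an opinion on causality written at the time. A reader might infer that every retrospective call is newly made with the patient's outcome known. The document does not support that, because it is silent. What stands is the silence: the two sources are not separated.

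A reader might also infer that knowledge of the Article 20 findings sets retrospective judgements apart. It does not. That review is already reported in section 7.1 of a protocol dated June 2017, so prospective assessors know its findings too.

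Nor do the documents support a claim that the strata will differ through hindsight alone. The split is a single calendar date, so an event just before it has a short lag. The synopsis has prospective data entered near the last visit, whereas 9.4 says near each visit, so some prospective events may also be judged late. Staff behaviour, thinner charts and the new product warnings described in 7.1 are other reasons for a difference.

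It can fairly be said that 9.3 may mean only that the same list of items is collected in both modes, and that 9.7 and 9.9 admit differential collection. That softens the wording problem. It does not remove it, because neither section names attribution as a source and stratifying cannot isolate it. The ENCePP checklist says that no comparisons will be made, so a rate ratio is not a planned estimate. Even so, the stratified rates are there to account for bias and will be read side by side.

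Finally, the format of stratum tables can be left to an SAP. The source and date of each causality call cannot, because no analysis plan can recover them if they are not recorded.

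**Conclusion.** The point holds as a gap in how causality is specified. ADR and SADR depend on an investigator judgement that, for the earliest EU events, can come about 3.3 to 3.6 years after the event, assuming assessment in Q1 2018. The protocol does not mark which calls were charted at the time. The sameness claimed in 9.3 does not hold for this variable, and stratifying ADR and SADR rates cannot separate attribution from documentation. Section 9.7 does not say which outcomes are stratified, so this consequence applies if the stratification uses the outcomes that section models.

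The size and direction of any shift in rates cannot be computed from the document, and there may be none. The effect is confined mainly to ADR and SADR and to HOIs whose collection depends on attribution. All-cause SAE rates under section 8 stand. This is a cheap and worthwhile improvement, not a flaw that undermines the primary objective.

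**What to change.** - **Section 9.7:** run the rate estimates and the retrospective/prospective stratified analysis on all-cause SAEs, which section 8 names but the Poisson and Cox models in 9.7 do not list. Add HOIs only where they are collected regardless of attribution. Show these beside the ADR and SADR results.
- **eCRF:** for each event, record the source of the causality assessment (charted at the time or assigned at abstraction) and its date.
- **Section 9.3:** qualify the sameness statement, and the restriction to routine-care data, for causality.
- **Section 9.9:** name differences in the timing and source of attribution as a possible bias.

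The cost is two short eCRF fields and one extra table, with no additional patients. Bounds that treat abstraction-assigned SAEs as all related and as all unrelated are optional. If every retrospective call were assigned at abstraction, they would run from zero to the full SAE rate in that stratum and say little.

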## **12. PLANS FOR DISSEMINATING AND COMMUNICATING STUDY RESULTS**

### **12.1. Study Report and Publications**

A study report will be prepared and provided to the applicable regulatory agencies. Gilead will ensure that the report meets the standards set out in the Guideline on Good Pharmacovigilance Practices (GVP) Module VIII. Note that an abbreviated report may be prepared in certain cases. The final study report will be submitted within 12 months of study completion.

Any study publication will be prepared and provided to the European Medicines Agency (EMA). In this case, Gilead Sciences will follow the standards set out in the STROBE Guidelines for Strengthening the Reporting of Observational Studies in Epidemiology (STROBE) {[von Elm 2008](#)}.

## 14. ANNEXES

Number	Document Reference Number	Date	Title
1	Annex 1	13 June 2017	ENCePP Checklist for Study Protocols
2	Annex 2	13 June 2017	Investigator Signature Page

**Annex 1. ENCePP Checklist for Study Protocols**

**Study title:** Non-interventional study to assess the safety profile of idelalisib in patients with refractory follicular lymphoma (FL)

**Study reference number:** GS-EU-313-4172

Section 1: Milestones	Yes	No	N/A	Section Number
1.1 Does the protocol specify timelines for				
1.1.1 Start of data collection 				6
1.1.2 End of data collection 				6
1.1.3 Study progress report(s)				6
1.1.4 Interim progress report(s)				6
1.1.5 Registration in the EU PAS register				6
1.1.6 Final report of study results.				6

Comments:

Study will be registered in the EU PAS register. No timelines given in the protocol.

Section 2: Research question	Yes	No	N/A	Section Number
2.1 Does the formulation of the research question and objectives clearly explain:				
2.1.1 Why the study is conducted? (e.g. to address an important public health concern, a risk identified in the risk management plan, an emerging safety issue)				7
2.1.2 The objective(s) of the study?				8
2.1.3 The target population? (i.e. population or subgroup to whom the study results are intended to be generalised)				9
2.1.4 Which hypothesis(-es) is (are) to be tested?				-
2.1.5 If applicable, that there is no a priori hypothesis?				-

Comments:

Safety study without hypothesis testing.

 Date from which information on the first study is first recorded in the study dataset or, in the case of secondary use of data, the date from which data extraction starts.

 Date from which the analytical dataset is completely available.

Section 3: Study design	Yes	No	N/A	Section Number
3.1 Is the study design described? (e.g. cohort, case-control, cross-sectional, new or alternative design)				9.1
3.2 Does the protocol specify whether the study is based on primary, secondary or combined data collection?				9.3
3.3 Does the protocol specify measures of occurrence? (e.g. incidence rate, absolute risk)				9.7
3.4 Does the protocol specify measure(s) of association? (e.g. relative risk, odds ratio, excess risk, incidence rate ratio, hazard ratio, number needed to harm (NNH) per year)				-
3.5 Does the protocol describe the approach for the collection and reporting of adverse events/adverse reactions? (e.g. adverse events that will not be collected in case of primary data collection)				9, 11

Comments:

Only incidence rates (crude and adjusted) will be calculated. No comparisons will be made

Section 4: Source and study populations	Yes	No	N/A	Section Number
4.1 Is the source population described?				9.2
4.2 Is the planned study population defined in terms of:				
4.2.1 Study time period?				6
4.2.2 Age and sex?				-
4.2.3 Country of origin?				9.2
4.2.4 Disease/indication?				9.2
4.2.5 Duration of follow-up?				9.1
4.3 Does the protocol define how the study population will be sampled from the source population? (e.g. event or inclusion/exclusion criteria)				9.2

Comments:

Results will distinguish for age and sex. But the population will not be specifically defined for both characteristics.

Section 5: Exposure definition and measurement	Yes	No	N/A	Section Number
5.1 Does the protocol describe how the study exposure is defined and measured? (e.g. operational details for defining and categorising exposure, measurement of dose and duration of drug exposure)				9.2

Section 5: Exposure definition and measurement	Yes	No	N/A	Section Number
5.2 Does the protocol address the validity of the exposure measurement? (e.g. precision, accuracy, use of validation sub-study)				9.3
5.3 Is exposure classified according to time windows? (e.g. current user, former user, non-use)				9.1
5.4 Is exposure classified based on biological mechanism of action and taking into account the pharmacokinetics and pharmacodynamics of the drug?				

Comments:

--

Section 6: Outcome definition and measurement	Yes	No	N/A	Section Number
6.1 Does the protocol specify the primary and secondary (if applicable) outcome(s) to be investigated?				8
6.2 Does the protocol describe how the outcomes are defined and measured?				9.3
6.3 Does the protocol address the validity of outcome measurement? (e.g. precision, accuracy, sensitivity, specificity, positive predictive value, prospective or retrospective ascertainment, use of validation sub-study)				9.9
6.4 Does the protocol describe specific endpoints relevant for Health Technology Assessment? (e.g. HRQoL, QALYs, DALYS, health care services utilisation, burden of disease, disease management)				-

Comments:

The safety analyses will have per definition an impact on disease management. However, this is not specifically discussed in the protocol.
--

Section 7: Bias	Yes	No	N/A	Section Number
7.1 Does the protocol describe how confounding will be addressed in the study?				9.9
7.1.1. Does the protocol address confounding by indication if applicable?				9.9
7.2 Does the protocol address:				
7.2.1. Selection biases (e.g. healthy user bias)				9.9, 10
7.2.2. Information biases (e.g. misclassification of exposure and endpoints, time-related bias)				9.9
7.3 Does the protocol address the validity of the study covariates?				-

Comments:

--

Section 8: Effect modification	Yes	No	N/A	Section Number
8.1 Does the protocol address effect modifiers? (e.g. collection of data on known effect modifiers, sub-group analyses, anticipated direction of effect)				9.9

Comments:

--

Section 9: Data sources	Yes	No	N/A	Section Number
9.1 Does the protocol describe the data source(s) used in the study for the ascertainment of:				
9.1.1 Exposure? (e.g. pharmacy dispensing, general practice prescribing, claims data, self-report, face-to-face interview)				9
9.1.2 Outcomes? (e.g. clinical records, laboratory markers or values, claims data, self-report, patient interview including scales and questionnaires, vital statistics)				9
9.1.3 Covariates?				9
9.2 Does the protocol describe the information available from the data source(s) on:				
9.2.1 Exposure? (e.g. date of dispensing, drug quantity, dose, number of days of supply prescription, daily dosage, prescriber)				9
9.2.2 Outcomes? (e.g. date of occurrence, multiple event, severity measures related to event)				9
9.2.3 Covariates? (e.g. age, sex, clinical and drug use history, co-morbidity, co-medications, lifestyle)				9
9.3 Is a coding system described for:				
9.3.1 Exposure? (e.g. WHO Drug Dictionary, Anatomical Therapeutic Chemical (ATC) Classification System)				9
9.3.2 Outcomes? (e.g. International Classification of Diseases (ICD)-10, Medical Dictionary for Regulatory Activities (MedDRA))				9
9.3.3 Covariates?				9
9.4 Is a linkage method between data sources described? (e.g. based on a unique identifier or other)				-

Comments:

Only the patient's medical records will be used. No linkage between data sources.
---

Section 10: Analysis plan	Yes	No	N/A	Section Number
10.1 Is the choice of statistical techniques described?				9.7
10.2 Are descriptive analyses included?				9.7
10.3 Are stratified analyses included?				9.9
10.4 Does the plan describe methods for adjusting for confounding?				9
10.5 Does the plan describe methods for handling missing data?				9.7
10.6 Is sample size and/or statistical power estimated?				

Comments:

--

Section 11: Data management and quality control	Yes	No	N/A	Section Number
11.1 Does the protocol provide information on data storage? (e.g. software and IT environment, database maintenance and anti-fraud protection, archiving)				9.6
11.2 Are methods of quality assurance described?				9
11.3 Is there a system in place for independent review of study results?				11, 12

Comments:

--

Section 12: Limitations	Yes	No	N/A	Section Number
12.1 Does the protocol discuss the impact on the study results of:				
12.1.1 Selection bias?				9.9
12.1.2 Information bias?				9.9
12.1.3 Residual/unmeasured confounding? (e.g. anticipated direction and magnitude of such biases, validation sub-study, use of validation and external data, analytical methods)				10.3
12.2 Does the protocol discuss study feasibility? (e.g. study size, anticipated exposure, duration of follow-up in a cohort study, patient recruitment)				9.2, 9.5

Comments:

--

Section 13: Ethical issues	Yes	No	N/A	Section Number
13.1 Have requirements of Ethics Committee/ Institutional Review Board been described?				10
13.2 Has any outcome of an ethical review procedure been addressed?				10
13.3 Have data protection requirements been described?				9, 10

Comments:

Section 14: Amendments and deviations	Yes	No	N/A	Section Number
14.1 Does the protocol include a section to document amendments and deviations?				5

Comments:

Section 15: Plans for communication of study results	Yes	No	N/A	Section Number
15.1 Are plans described for communicating study results (e.g. to regulatory authorities)?				12
15.2 Are plans described for disseminating study results externally, including publication?				12

[figure not shown]
Comments:

